6.4.3. Serious Adverse Events

A Serious Adverse Event is an Adverse Event that leads to death or to serious deterioration in the health of the participant that either resulted in a life-threatening illness or injury, or a permanent impairment of a body structure or body function.

6.5.Lost to Follow-Up

If a participant fails to provide event information via the study/patient portal 30 days after the start of the trial, the remote coordinator will attempt to contact the participant to ascertain whether or not the participant has had a cold or not and if the participant wishes to and/or should continue in the study.

Before a participant is deemed lost to follow up, the investigator or designee must make every effort to regain contact with the participant (where possible, 3 telephone calls and, if necessary, a certified letter to the participant's last known mailing address or local equivalent methods). These contact attempts should be documented in the participant's study record.

Should the participant continue to be unreachable, he/she will be considered to have withdrawn from the study and the study exit form will be completed.

6.6.Test Product Packaging/Handling/Storage/Accountability

- The 18-day supply of test product (36 packets) will be packaged and labeled with a study ID number.
- Participants will receive guidance on how to report receipt, store, and use the test product.
- Hawthorne Effect Inc. will support storage and shipment of test product, documentation of test product assignment, and completion of test product accountability.

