6.4. Adverse Event and Safety Monitoring

Adverse Events (AEs) are defined as any untoward medical occurrences described by the study participant. All AEs will be self-reported and documented on the platform. The AEs will be reviewed by the study team including the remote trial coordinator and study principal investigator and reported according to the IRB requirements. Participants who experience adverse events will be advised to stop taking the test product and seek medical attention.

In the event that a participant experiences an adverse event, the clinical study manager or clinical ops coordinator will notify both the PI and Sponsor. The Sponsor will take appropriate action according to their standard operating procedures for any adverse events that warrant action by the sponsor.

6.4.1.Anticipated Adverse Events

Anticipated Adverse Events are complications that are known to be associated with the test product (in high doses exceeding recommended use):

- epigastric pain
- nausea
- vomiting
- loss of appetite
- abdominal cramps
- diarrhea
- headaches

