6.4.2. Adverse Event Relationship

Each reported AE will be assessed by the Investigator for relatedness, severity and causality.

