7.1. Study Outcomes Measures

Analysis populations:

The *intent to treat* (ITT) population consists of all participants who are consented, report the onset of cold symptoms, and have taken the test product at least once. The primary analysis will be in the ITT population.

Primary Endpoint:

• The primary endpoint will be time to freedom from cold symptoms, with the clock starting at the onset of the cold. Where the onset is defined as the point in time when the participant experiences 2 or more cold symptoms. The primary analysis will be a Kaplan-Meier analysis of time to absence of all symptoms, based on the participant's self-report. There is no control group for the primary analysis.

Secondary Endpoints:

- Secondary endpoints involve the duration and severity of the separate cold symptoms.
- Comparison against the participant's normal behavior.
- Net Promoter Score.
- Adverse events will be summarized.
- An additional data presentation will consist of results from both Treatment and Control in similar studies appearing in the literature. There will be no formal statistical comparison of results from this study and historical studies.

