13.1.7. Appendix G Adverse Event Form

Immune AE document

- 1. Did you experience any side effects after taking the test product? Y/N
 - a. If so, did you experience any of the following
 - o itching, rash, hives, throat/lip/tongue swelling, wheezing
 - low blood pressure, fainting, chest pain, shortness of breath, palpitations, irregular heart beat
 - o severe, persistent nausea, vomiting, diarrhea, or abdominal pain
 - o difficulty urinating, decreased urination
 - o fatigue, appetite loss, yellowing skin/eyes, itching, dark urine
 - severe joint/muscle pain
 - o slurred speech, one-sided weakness of face, arm, leg, vision
 - o abnormal bleeding from nose or gums
 - o blood in urine, stool, vomit,
 - o marked mood, cognitive, or behavioral changes, thoughts of suicide
 - o Other:
- 2. Please give a description of the event
- 3. How soon after taking the test product did you experience the side effect?
- 4. What did you do to alleviate the side effect?
- 5. Did you have to go to the hospital or see a doctor for this side effect?
 - a. Please describe any diagnosis or treatment that they provided.
 - b. If you were seen in the hospital, please upload any discharge paperwork or other documents from the hospital.

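### The serious adverse event definition in section 6.4.3 leaves out a hospital admission that is neither life-threatening nor permanently impairing, although Appendix G asks for the hospital paperwork

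*Combined protocol and SAP*

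**What the plan says.** Section 6.4.3 opens: "A Serious Adverse Event is an Adverse Event that leads to death or to serious deterioration in the health of the participant". It then limits which deteriorations qualify: "that either resulted in a life-threatening illness or injury, or a permanent impairment of a body structure or body function". Hospital admission does not appear there, and no other section of the protocol adds it as a criterion of seriousness.

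The adverse event form (Appendix G, item 5) asks the participant: "Did you have to go to the hospital or see a doctor for this side effect"? Item 5a asks for any diagnosis or treatment. Item 5b adds: "If you were seen in the hospital, please upload any discharge paperwork or other documents from the hospital".

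On handling, section 6.4 says that adverse events are reviewed by the study team, including the principal investigator, and "reported according to the IRB requirements". The principal investigator and the sponsor are both notified. Section 6.4.2 says: "Each reported AE will be assessed by the Investigator for relatedness, severity and causality". Seriousness is not among the things assessed.

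On analysis, section 7.1 lists under the secondary endpoints: "Adverse events will be summarized". Section 7.3 says no more than this about adverse events.

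**The concern.** The plan asks for hospital documents but has no stated step at which they bear on whether an event is serious. This matters more here than in a clinic-based trial. Participants stay at home, any contact is remote, and the Limitations section (section 11) concedes that the study depends on self-report without medical review of symptoms. Hospital papers are the only third-party clinical record that the protocol says it will request. Section 6.4 also advises participants with adverse events to seek medical care, so some hospital contact is foreseeable.

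At stake is the accuracy of the safety summary. Section 10 says that the results will be submitted for publication, and the synopsis says that the data may be used to design a two-arm trial. A reader told that there were no serious events would probably not expect the database to contain an inpatient discharge summary. Under section 6.4.3 as written, both could be true.

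**Working it through.** This is a question of wording, so the check is to apply the definition to the kinds of event that the form could bring in.

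**Step 1. Is the list closed?** Section 6.4.3 has two limbs: death, and serious deterioration. The second limb is qualified by an either/or with two members, threat to life and permanent impairment. There is no residual category such as other medically important events.

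**Step 2. Apply it.**

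| Event | Class under 6.4.3 | What Appendix G item 5 holds |
|---|---|---|
| Death | Serious | Not applicable (self-report) |
| Admitted, life-threatening, full recovery | Serious | Yes to 5, papers under 5b |
| Admitted, permanent impairment | Serious | Yes to 5, papers under 5b |
| **Admitted, not life-threatening, full recovery** | **Not serious** | **Yes to 5, papers under 5b** |
| Emergency visit without admission, not life-threatening, full recovery | Not serious | Yes to 5, papers under 5b |
| Doctor's visit only, not life-threatening, full recovery | Not serious | Yes to 5, no hospital papers |

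The gap is the fourth row.

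**Step 3. Can the form identify the fourth row?** Not directly. Item 5 puts hospital and doctor into one question, and item 5b refers to having been seen in hospital, which covers an emergency visit as well as a stay. Rows four and five give the same answers. Only the uploaded papers, or free text under item 5a, could separate them.

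**Step 4. Does another step catch it?** Section 6.4.2 covers relatedness, severity and causality. Severity grading may well reflect a hospital stay, but a severe event is not made serious by that grade under section 6.4.3.

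**Step 5. Reach of the form.** Appendix G asks about side effects after taking the product, and diary item 11 (Appendix E) asks only whether a doctor was seen. An admission for the cold itself may not be recorded on either form.

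**Step 6. Size.** The plan gives no adverse event or admission rate, so there is no figure of its own to reproduce. The intended number treated is 200 × 0.40 = 80 (sections 5.1 and 7.2). If exactly one treated participant had an event of the fourth kind, the serious-event proportion would be 1/80 = 1.25% with admission as a criterion and 0/80 = 0% without it. The single event is assumed for illustration and is not a forecast.

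**The case against.** The strongest reply is that little in the plan depends on the label. There is no serious-event endpoint, table, reporting timeline or stopping rule tied to section 6.4.3. The analysis text promises only a summary of adverse events. The event would still reach the investigator and the sponsor and would still be graded, and the hospital papers are natural source material for that grading. Collecting them for severity does not contradict a narrower definition of seriousness, and the documents never say that Appendix G is meant to decide seriousness. All of this stands, and it limits the point to classification.

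Four stronger readings are tempting, and the documents do not support them:

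- *Any hospitalised participant would be counted as non-serious.* An admission for a life-threatening reaction is already covered, even with full recovery.
- *Hospital information is ignored.* Sections 6.4 and 6.4.2 provide for review and severity grading of every reported event.
- *Appendix G already captures admission, so one phrase in 6.4.3 is enough.* Item 5 merges hospital and doctor and does not ask about an inpatient stay.
- *An expedited report would be missed.* No expedited route for serious events is described, so this can be neither shown nor excluded.

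It may also be said that the protocol commits itself to GCP, federal regulations and IRB requirements, which might supply a wider definition. The protocol cites these but does not reproduce their definitions of seriousness. They cannot settle the matter either way here, and a study team would naturally apply the definition that the protocol gives.

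**Conclusion.** The gap is real but narrow. As written, section 6.4.3 classes a non-life-threatening, fully resolving hospital admission as non-serious while Appendix G requests the paperwork that would document it. Any count of serious events in the adverse event summary could be understated for that reason. The reporting, review and severity grading of the event are not affected, nor are the sample size and the primary Kaplan-Meier analysis.

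The size cannot be stated from the documents. The contrast of 1/80 with 0/80 shows only that one event is enough to change the sentence a reader would see. A reader should not take 1.25% as an expected understatement.

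The conclusion assumes that the study team applies section 6.4.3 literally, and that the adverse event summary will distinguish serious from other events. The plan states neither. Section 7.3 leaves analysis detail to a later SAP, which could introduce such a table.

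**What to change.** Reconcile section 6.4.3 with Appendix G through three linked edits:

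1. **Section 6.4.3:** add inpatient hospital admission as a criterion of seriousness. At the same time, check the rest of the definition against the GCP standard named in the Statement of Compliance.
2. **Appendix G, item 5:** split the question so that a doctor's visit, an emergency visit without admission, and an inpatient admission are recorded separately. Keep the request for papers.
3. **Section 6.4.2:** add seriousness to the investigator's assessment, made against 6.4.3 with any uploaded papers in hand.

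The first edit alone would create a criterion that the form does not measure, so the three should be made together.

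The cost is one phrase in a definition, one form item and one more classification for each adverse event. The serious-event count may also come out less favourable. No change to the sample size or to the efficacy analysis is needed.

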6.7. Study Management

This study uses a decentralized clinical trial format to foster inclusivity, diversity and accessibility for a broad study population and to ensure efficiencies for enrollment and study data collection. The study will be managed using an end to end virtual clinical trial platform called Hawthorne Effect Study Visit Management Platform which is designed to make participant participation in clinical trials more accessible and as least burdensome as possible. The Hawthorne Effect platform (www.hawthorne-effect.com) is GCP/ICH/21CFR and HIPAA compliant. Hawthorne Effect uses a network of specialty vetted and trained healthcare professionals, or HEROs who are study investigators, screeners and conduct personalized patient visits for screening and follow-up. For this trial, the Hawthorne Effect study visits will be virtual, and the platform will be used to collect patient reported outcomes and to track screening, enrollment and study compliance.

7. Statistical Considerations

7.1. Study Outcomes Measures

Analysis populations:

The *intent to treat* (ITT) population consists of all participants who are consented, report the onset of cold symptoms, and have taken the test product at least once. The primary analysis will be in the ITT population.

Primary Endpoint:

• The primary endpoint will be time to freedom from cold symptoms, with the clock starting at the onset of the cold. Where the onset is defined as the point in time when the participant experiences 2 or more cold symptoms. The primary analysis will be a Kaplan-Meier analysis of time to absence of all symptoms, based on the participant's self-report. There is no control group for the primary analysis.

Secondary Endpoints:

- Secondary endpoints involve the duration and severity of the separate cold symptoms.
- Comparison against the participant's normal behavior.
- Net Promoter Score.
- Adverse events will be summarized.
- An additional data presentation will consist of results from both Treatment and Control in similar studies appearing in the literature. There will be no formal statistical comparison of results from this study and historical studies.

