2.2.3. Minimization of Risks

Research participants will be carefully screened to meet enrollment criteria. Participants meeting exclusion criteria will not be enrolled. The study participant informed consent will be presented with clear description of the study requirements and opportunity to have questions answered before enrollment will be provided. Once an event occurs, review of symptoms will be

ascertained daily until symptoms have resolved or for 18 days. Reporting of adverse events will be reviewed routinely and in accordance with regulatory guidelines (21CFR, GCP) by the Principal Investigator. Participants with occurrence of worsening symptoms or adverse events will be advised to stop the product and may seek medical attention and exit the study.

3. Study Objectives

The purpose of the present study is to evaluate 1) the impact of the Immune Support test product on the duration of symptoms of the common cold in adult participants and 2) the subjective experience of these participants related to general health, common cold symptoms, and personal experience with the product. [13, 18, 29, 32]

This will be evaluated based on the primary and secondary endpoints. These endpoints, the analysis populations, and their respective measures are described below. Further details on the methods for measuring the outcomes can be found in the Study Outcome Measures and Analysis Plan sections.

Primary Endpoint:

The primary endpoint will be time to freedom from cold symptoms, with the clock starting at the onset of the cold. Where the onset is defined as the point in time when the participant experiences 2 or more cold symptoms. The primary analysis will be a Kaplan-Meier analysis of time to absence of all symptoms, based on the participants' self-report. There is no control group for the primary analysis. [5]

Secondary Endpoint:

- Secondary endpoints involve the duration and severity of the separate cold symptoms.
- Comparison against the participant's normal behavior.
- Net Promoter Score.
- Adverse events will be summarized.
- An additional data presentation will consist of results from both Treatment and Control in similar studies appearing in the literature. There will be no formal statistical comparison of results from this study and historical studies.

4.Study Design

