The present study will be a single site, prospective, single arm observational study of minimal risk consisting of at least 200 participants who suffer from cold symptoms. The participants must meet additional inclusion/exclusion criteria (see Inclusion/Exclusion Criteria). Participants will begin taking the powder drink-mix at the onset of their cold symptoms. Onset is defined as the point in time the participant experiences 2 or more cold symptoms (cough, hoarseness, muscle ache, nasal drainage,

nasal congestion, scratchy throat, sore throat, sneezing, or an oral temperature greater than 37.7 °C (99.9 °F)). When the participant experiences 2 or more symptoms, they will report symptoms in the cold start form. If they meet the criteria for a cold, they will start completing the daily cold symptom diary prior to taking the test product. After consuming the product, the participant will complete the cold symptom diary daily until all symptoms resolve. Since none of the ingredients in the test product have been seen to provide relief from fever or pain, the participant will be allowed to take a pain reliever and fever reducer (e.g. ibuprofen or acetaminophen). If medication is taken, the participant will record this in their symptom diary.

Study enrollment and management will be decentralized, where participants do not visit an investigator or a clinic for clinical assessment. The participants will participate in the study at home. All data collected from during this study will be reported by the participant via eCRFs, eDiary, and other electronic data entries. If a visit is required, it will be conducted via remote contact by telephone.

4.1.Test Product

Overview:

Participants in this study will consume the test product twice a day (4-6 hours apart) at the onset of cold symptoms. The participant will mix one packet of the test product in 6-8 ounces of water. The test product will be delivered to the participants' residence in a single shipment consisting of an18-day supply (36 packets) of the test product. The study participant will mix the contents of the packet into 6-8 oz. of hot water and drink twice a day during the duration of the cold.

Below is the description of the test product and its ingredients.

Test Product

Description: Combining whole food sourced Vitamin C, Echinacea, Ivy Extract, Zinc, Ginger and Turmeric. This formula is designed to support the immune system while reducing the duration of cold.

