- At time of enrollment, participant will be given access to the HIPAA compliant study portal.
 - The study portal provides access to study information, signed informed consent form, instructions for product use, frequently asked questions, study surveys, symptom diary, and data collection tools.
- Participant shall complete baseline assessments upon access to the portal.
 - Baseline assessment will include questions regarding the participants' demographics, medications, detailed information regarding previous colds, including treatment.
- To ensure that baseline assessments are completed before test product is used by the
 participant, study materials and study welcome package will be shipped to the participant once
 the clinical study manager/clinical operations coordinator confirms that the baseline assessment
 has been completed.
- The welcome package will include an information sheet that will outline instructions for their participation in the trial, the test product, disposable thermometer, and paper forms of the

- documents (paper form of study documents will be provided for real time data collection, in the event that the participant cannot log into the study portal to input data).
- Once the participant receives the test product, the participant will log into the study portal to acknowledge the receipt of the test product.
- Study start date will be the date of acknowledgement of receipt of test product.
- Participant will be sent weekly email reminders that remind them of their participation in the study. Once the participant indicates they are experiencing a cold. The participant will be reminded by email daily to complete their symptom diary.
- At the onset of their cold symptoms, the participant will complete the cold start form.
 - Onset is defined as the point in time the participant experiences 2 or more cold symptoms (cough, hoarseness, muscle ache, nasal drainage, scratchy throat, sore throat, sneezing, oral temperature greater than 37.7°C (99.9 °F)).
 - If fever is a symptom that the participant experiences, they will use the provided disposable thermometer to take their temperature and record it in the diary.
- If the participant meets all the criteria for a cold, they will start their symptom diary prior to taking the test product.
- After completing the surveys, the participant will take the test product. The participant will mix 1 drink-mix packet into 6-8 oz of water and consume the whole drink.

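### The primary Kaplan-Meier clock starts at cold onset, but entry to the set requires a dose; if some participants dose late, duration is biased upward, and the plan neither corrects nor reveals it

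*Combined protocol and SAP*

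**What the plan says.** On the time origin, Section 7.1 has the primary endpoint run "with the clock starting at the onset of the cold", and "the onset is defined as the point in time when the participant experiences 2 or more cold symptoms". The synopsis and Sections 3 and 4.4 use the same origin.

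On who is counted, the intent-to-treat population of Section 7.1 "consists of all participants who are consented, report the onset of cold symptoms, and have taken the test product at least once", and the primary analysis is done in that set.

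On the method, "The primary analysis will be a Kaplan-Meier analysis of time to absence of all symptoms, based on the participant's self-report", and "There is no control group for the primary analysis". The censoring rules in Section 7.3 cover participants without a cold, incomplete diaries, symptoms persisting at 18 days, and withdrawal. They contain no delayed entry, no landmark, no maximum gap from onset to first dose, and no rule for a cold that ends before dosing. The algorithms are to be the defaults of the R survival package.

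On when the first dose is due, Section 4 states "Participants will begin taking the powder drink-mix at the onset of their cold symptoms". Section 6.1 orders the steps as cold start form, diary, then product. The schedule in Section 6.2 marks product consumption on the event start date, and Appendix B also places the first packet at symptom onset.

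On compliance, Section 7.2 speaks of uncertain compliance and Section 11 concedes that nothing independent checks it. Until a cold is reported, the routine prompt in Section 6.1 is weekly: "Participant will be sent weekly email reminders that remind them of their participation in the study".

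**The concern.** Membership of the analysis set depends on an act, taking a first dose, that can come after time zero. A participant who reports onset and recovers before dosing never enters. One who first doses on day *d* is counted at risk from day 0, although a recovery before day *d* would normally have kept that person out. This is left truncation, often called immortal time. An ordinary Kaplan-Meier curve then has too many people at risk and too few recoveries in the early days, so it sits too high.

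The affected quantity is the trial's one primary estimate. No concurrent arm shares the error, so nothing cancels it. The estimate is to be shown beside published arms and may inform a two-arm trial. Increasing enrollment, as Section 5.1 allows, would shrink the sampling error but not this bias. The analyses the protocol lists include neither the delay nor the number of reported colds never dosed, so a reader could not tell whether the bias had occurred.

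The label matters separately. A set conditioned on having taken treatment is a treated set. Sections 5.1 and 7.2 themselves speak of treated participants.

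**Working it through.** **The plan's own figure.** Section 7.2 expects 40% of 200 enrolled to have a cold: 200 × 0.40 = 80. This reproduces exactly. No power, alpha or precision target is given for the primary endpoint.

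**Inputs.** From the documents: origin at onset, at least one dose required, censoring at 18 days, 80 colds. Assumed, because the documents are silent: Weibull durations with shape *k* = 1 or 2, a true median of 7 days, the delay patterns below, and delay independent of how long the cold would last.

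**Formula.** Let S(t) = exp(−(t/λ)^k), with λ = 7/(ln 2)^(1/k). This gives λ = 10.10 for k = 1 and 8.41 for k = 2. A cold is counted only if it outlasts the delay, so the included fraction is A = Σ p_d S(d). Beyond the longest delay, survival in the included set is S(t)/A. The naive median therefore solves S(m) = A/2:

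m = λ (ln 2 − ln A)^(1/k)

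**Everyone doses on day 0.** A = 1 and m = 7. The bias is zero.

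**80/10/7/3% dose on day 0/1/2/3.**
- k = 1: S(1), S(2), S(3) = 0.906, 0.820, 0.743. A = 0.8 + 0.1(0.906) + 0.07(0.820) + 0.03(0.743) = 0.970. m = 10.10 × (0.693 + 0.030) = 7.30.
- k = 2: S(1), S(2), S(3) = 0.986, 0.945, 0.880. A = 0.991. m = 8.41 × √(0.693 + 0.009) = 7.04.

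**Half dose at once, half evenly over 0 to 7 days.** Here A = 0.5 + 0.5 × (mean of S over 0 to 7).
- k = 1: mean S = 0.721, A = 0.861, m = 10.10 × (0.693 + 0.150) = 8.52.
- k = 2: mean S = 0.810, A = 0.905, m = 8.41 × √(0.693 + 0.100) = 7.49.

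| Delay pattern (assumed) | Colds never counted | Naive median | Shift |
|---|---|---|---|
| All on day 0 | 0% | 7.0 | 0 |
| 80/10/7/3% on days 0/1/2/3 | 0.9 to 3.0% | 7.04 to 7.30 | 0.04 to 0.3 d |
| 50/25/15/10% on days 0/1/2/3 | 2.4 to 7.6% | 7.12 to 7.80 | 0.1 to 0.8 d |
| Half at once, half over 0 to 7 d | 9.5 to 13.9% | 7.49 to 8.52 | 0.5 to 1.5 d |

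The upper end of each range comes from k = 1, a constant recovery hazard, under which early recovery is more common.

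**Scale.** The large-sample standard error of a median is 1/(2 f(m) √n), with f(m) = 0.5 k ln 2 / 7. For n = 80 this is 1.13 days (k = 1) and 0.56 days (k = 2).

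**Does delayed entry repair it?** In simulations of 400,000 colds with true medians of 4.5, 5.5 and 7.5 days, under the 95/5% (day 0/1), 80/10/7/3% and 50/25/15/10% patterns, Kaplan-Meier with entry at first dose came within about 0.02 days of the true median every time.

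**The case against.** The strongest reply is that the protocol leaves no planned gap. Product is in hand before the study start date, people unwilling to try it are excluded, and the first dose is directed at onset, straight after that day's diary. With one diary a day, same-day dosing leaves no earlier day on which a missed recovery could have been recorded. This stands. A reader might infer from the structure that the primary estimate is bound to be too long; the documents do not support that, because the bias exists only to the extent that people dose late. Nor is the pre-dose interval strictly recovery-free: Section 7.1 does not require the first dose to precede recovery, although a first dose after recovery should be rare.

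The weekly email is also weak evidence of long delays. It reminds people that they are in the study and is not what triggers dosing. Someone who forgets may also file the cold start form late. That form is not in the text available, so it cannot be seen whether the recorded onset is back-dated. If the filing date became day 0, the forgotten days would be off the clock and the recorded duration would be too short. The upward direction therefore holds for a gap between the onset used in the analysis and the first dose, not for every kind of lateness. People may also go undosed for reasons other than early recovery, so the net selection effect cannot be fixed from the documents.

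Finally, there is no formal comparison with historical studies, and detail is deferred to a later SAP that could specify delayed entry. Both are true, and they limit the consequences. They do not remove the case for specifying it, since the protocol concedes that compliance is uncertain and unchecked.

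**Conclusion.** The structure is in the text: the origin at onset precedes a dose-based entry condition, and nothing in the analysis plan handles a gap between them. Whether it biases the result depends on behavior that the documents do not describe. With same-day dosing the bias is nil. With mostly prompt dosing the shift in a 7-day median is well below the sampling error. It becomes comparable to that error only if about half of participants start late. These sizes rest on the assumed Weibull durations, delay patterns and independence of delay and duration.

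A reader might also infer that the analysis could manufacture a benefit. It could not by this route: colds would look longer, which counts against the product in the side-by-side display. The harm would be a distorted duration carried into planning. Severity is minor unless late dosing proves common. The label intent to treat is wrong whatever the delay.

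**What to change.** 1. Rename the set *treated population*.
2. Make sure the date of first dose is captured. The daily diary in Appendix E has no item for it; the cold start form could not be checked.
3. Tabulate the onset-to-first-dose delay and the number of reported colds never dosed.
4. Fit the Kaplan-Meier curve on time from onset with entry to the risk set at first dose, at minimum as a prespecified sensitivity analysis beside the naive curve. The two coincide if all dose on the day of onset. Use the first diary entry as the entry time only where the first dose followed that diary the same day; otherwise the truncation remains.
5. Show all reported onsets, dosed or not, as a check.
6. State the assumption that delay is unrelated to how quickly the cold would resolve.

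The cost is SAP wording, one date if it is not already captured, a little more analysis, and slightly smaller early risk sets. The survival package named in the plan supports delayed entry, and no further participants are needed.
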